4.3.2 LIKELIHOOD OF LARGE ESOPHAGEAL VARICES (CLD VALIDATION DATASET)

The analytical and statistical methods described in this section apply to the **primary and secondary objectives**. The steps in this analysis are similar to those used for analysis of the HALT-C Training Dataset:

- 1. Uni-variable Logistic Regression. Univariate logistic regression analysis will be performed using DSI as the independent variable and large varices as the outcome. (see **Table 3** for example of the output from this analysis).
- 2. Multi-variable Logistic Regression. As presented above, the gold standard for varices risk by AASLD guidelines is a liver biopsy diagnosis of cirrhosis. In BAVENO VI, platelet count was another major modifier of risk for clinically significant portal hypertension and risk for varices. Risk for large varices also correlates with CP class. For these reasons, we will evaluate the independence of DSI as a predictor after taking these variables into account. (see Table 4 for example of the output from this analysis).
- Receiver Operator Curve (ROC) analysis. The diagnostic performance of DSI for predicting large varices will be evaluated by Area under the Receiver Operating Curve (AUROC) and c-statistic. The optimum performance characteristics will be defined by Youden Index and sensitivity, specificity, PPV, NPV, NLR,

FNR, miss rate⁵ and 95% CIs will be defined over the spectrum of the findings (see **Figure 3** for an example of output from this analysis).

4. **Probability and Calibration Curves.** The plot of predicted probability of large varices versus DSI will be analyzed by linear regression and correlation coefficients and displayed along with 95% confidence intervals (see **Figure 4** and **5** and **Table 5** for example of the output from this analysis).

The diagnostic performance (sensitivity, specificity, PPV, NPV, NLR, FNR, miss rate⁵) of DSI cutoff 18.3 will be evaluated for large esophageal varices. In addition, we will define the relationship of DSI to the probability of large esophageal varices over the full range of DSI.

An exploratory objective is to examine the diagnostic performance of DSI cutoff 18.3 for large varices compared to the diagnostic performance of a range of DSI cutoffs bracketing DSI 18.3. We will examine, in 0.5 increments of DSI, DSI's diagnostic performance (sensitivity, specificity, PPV, NPV, NLR, FNR) from 13 to 23 to define the Optimal DSI for "Rule Out" – highest sensitivity and NPV with lowest FNR. We will also compare the diagnostic performance of this "optimum" DSI to the DSI chosen for validation, DSI 18.3. The purpose of this analysis is to provide upside and downside performance of DSI around the validated cutoff of DSI 18.3. This analysis will yield a table of sensitivities, specificities, NPVs, PPVs, NLRs, and FNRs over the given range of DSI that could be included in a package insert to help the clinician interpret a given DSI result., as defined from AUROC analysis and Youden Index.

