9.6.2 EXPLORATORY ANALYSES

Exploratory 1 (AUROC of DSI for large esophageal varices): The c-statistic for the AUROC for DSI in likelihood of large esophageal varices will be compared to the c-statistic for the AUROC of LSM plus platelet count in likelihood of large esophageal varices. The most complete study with publication of AUROCs for LSM plus platelet count is from Abraldes, et al (8) where the AUROC was 0.76 for varices needing treatment (large varices or small varices with red signs). Given this benchmark the performance goal is an AUROC \geq 0.76 for DSI in likelihood of large esophageal varices.

In addition, we will examine the diagnostic performance (sensitivity, specificity, PPV, NPV, NLR, PLR, FNR, miss rate⁸) of DSI over the full range of DSI to define the Optimal DSI for "Rule Out" – highest sensitivity and NPV with lowest FNR. We will also compare the diagnostic performance of this "optimum" DSI to DSI 18.3. The purpose of this analysis is to provide upside and downside performance of DSI around the validated cutoff of DSI 18.3.

This analysis will yield a table of sensitivities, specificities, NPVs, PPVs, NLRs, PLRs, FNRs, and miss rates⁸ over the given range of DSI that could be included in a package insert to help the clinician interpret a given DSI result.

AUROCs of DSI in likelihood of large varices will be constructed for individual etiologies of disease with over 100 subjects and for the categories of cholestatic and non-cholestatic liver diseases.

Exploratory 2 (DSI for Small or Any Size of Esophageal Varices). The analyses listed above for primary objective, secondary objective 1, and secondary objective 2 will be repeated using small varices in one set of analyses and any size of varices in another set of analyses.

Exploratory 3 (STAT). The serum concentration of d4-cholate from the 60-minute time point (STAT) of the HepQuant SHUNT test correlates well with DSI (r^2 =0.88). The STAT value represents a simplified, single point version of DSI. For this reason, we propose to evaluate the diagnostic performance of a cutoff for STAT defined from the HALT-C Training dataset for large esophageal varices and esophageal varices of any size.

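### The exploratory optimum DSI cutoff is chosen and scored on the same validation subjects, with no optimism correction, before it is compared with the prespecified 18.3

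*Combined protocol and SAP*

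**What the plan says.** The primary test concerns only DSI 18.3, which was fixed from HALT-C. Exploratory objective 1 (Sections 1.1, 3 and 9.6.2, with method in Section 4.3.2) adds a search for a better rule-out cutoff in the validation dataset.

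- **Rule.** Section 4.3.2 gives two: "The optimum performance characteristics will be defined by Youden Index", in the ROC step, and "highest sensitivity and NPV with lowest FNR", in the exploratory paragraph. That paragraph ends by returning to the Youden index. Sections 1.1 and 9.6.2 use only the sensitivity/NPV/FNR wording. None says how ties are resolved.
- **Range.** Section 4.3.2 searches in steps of 0.5 "from 13 to 23 to define the Optimal DSI for" rule-out. Section 9.6.2 speaks "of DSI over the full range of DSI to define the Optimal DSI for" rule-out.
- **Comparison.** The optimum is compared "to the DSI chosen for validation, DSI 18.3", in the same subjects.
- **Status and use.** Section 4.3.2 calls it exploratory: "An exploratory objective is to examine the diagnostic performance of DSI cutoff 18.3 for large varices". The resulting table is one "that could be included in a package insert to help the clinician interpret a given DSI result".

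Section 4.3.2 plans 95% CIs across cutoffs but no adjustment for selection. Section 9.3 names no other dataset for sensitivity analyses.

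**The concern.** A cutoff picked because it performed best in a sample partly reflects chance in that sample. Scored on the same people, it looks better than it would in new patients. The comparator, 18.3, was not chosen on these data and carries no such bias, so the contrast tilts towards the selected cutoff.

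The plan avoids this elsewhere. DSI 18.3 was set in HALT-C and is tested here, and Section 4.3.4 treats the STAT cutoff the same way. Only the optimum DSI is chosen and scored on one dataset.

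At stake is an exploratory figure that might reach labelling. An NLR shown too low understates the odds of large varices after a negative result at that cutoff.

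**Working it through.** **1. The plan's own figure.** Section 9.2.1 assumes sensitivity 0.90, specificity 0.50, 80 cases and 320 non-cases. Table 9, equation E gives V = 0.9/(0.1×80) + 0.5/(0.5×320) = 0.1125 + 0.0031 = 0.1156, so SE = 0.340. Power = Φ(ln(0.52/0.20)/0.340 − 1.96) = Φ(2.81 − 1.96) = 0.802 (stated 0.80). Critical value = 0.52 × exp(−1.96×0.340) = 0.267 (stated 0.27). Both reproduce.

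**2. Models for DSI.** The plan gives no figure for selection optimism, so it was simulated with DSI normal in cases and in non-cases.

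- *Model 1, from HALT-C counts.* Table 2 puts 106/195 non-cases and 1/22 cases at or below 18.3. Table 5 puts 148/195 and 6/22 below predicted probability 0.10. By Table 3 that is DSI (6.4682 − 2.1972)/0.1947 = 21.94. Solving gives non-cases N(17.63, SD 6.13) and cases N(23.96, SD 3.35). The implied AUROC is Φ(6.33/√(6.13² + 3.35²)) = 0.818 (stated 0.82). It was repeated with both groups recentred to sensitivity 0.90 and specificity 0.50 at 18.3.
- *Model 2, built separately.* (A) fitted to the Table 5 counts, AUROC 0.83; (B) 0.95/0.54 at 18.3, AUROC 0.82; (C) 0.90/0.50, AUROC 0.79.

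Each simulated trial picks the optimum on the grid 13 to 23 by 0.5 (21 cutoffs; 18.3 is not one of them). Its same-sample result is then set against its true value. At 20% prevalence N=400 has 80 cases and N=250 has 50.

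**3. Results (averages over trials).**

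| Rule | N | Sensitivity, apparent minus true | NLR |
|---|---|---|---|
| Youden | 400 | +2.3 to +3 points | 0.035 to 0.047 too low |
| Youden | 250 | +3 to +4 points | about 0.05 to 0.064 too low |
| Highest NPV/lowest FNR, ties to highest cutoff | 400 | about +1 point | Model 1: 0.002–0.008 apparent, 0.025–0.039 true; Model 2: 0.002–0.040 apparent, 0.026–0.077 true |
| Same | 250 | +1.7 to +1.8 points (Model 2) | Model 2: 0.002–0.037 apparent, 0.038–0.089 true |
| Highest sensitivity, ties to lowest cutoff | either | none (always picks 13) | none |
| Fixed 18.3 | either | none | none |

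For example, setting C:

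- Youden, N=400: sensitivity 0.797 − 0.769 = 0.028; NLR 0.339 − 0.296 = 0.043.
- Youden, N=250: sensitivity 0.806 − 0.770 = 0.036; NLR 0.337 − 0.281 = 0.056.
- NPV rule, N=400: sensitivity 0.989 − 0.979 = 0.010; NLR ratio 0.040/0.077 = 0.52.
- NPV rule, N=250: sensitivity 0.990 − 0.972 = 0.018; NLR ratio 0.037/0.089 = 0.42.

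**4. The contrast with 18.3.** In setting C at N=400 the NPV-rule cutoff has a true NLR advantage over 18.3 of 0.200 − 0.077 = 0.123. The apparent advantage is 0.200 − 0.040 = 0.160, which is 0.037/0.123 = 30% too large. The advantage comes from a lower cutoff, with specificity about 0.26 against 0.50.

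**5. How likely N=250 is.** Section 9.5.1 analyses all endpoints at N=250 if the trial stops. Table 13 (sensitivity 0.90, 20% prevalence) gives a chance of stopping there for efficacy of 0.652 at NLR 0.20 and 0.880 at NLR 0.15.

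**The case against.** The case for leaving the plan alone has real force, and most of it stands.

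- *A reader might infer that the whole table is biased.* It is not. The rows of the 13-to-23 grid are fixed in advance, and each is free of selection bias for its own cutoff. Only the one named as optimum is affected.
- *A reader might infer that the selected cutoff will look better than 18.3.* Under Youden it usually does not on these measures. In Model 1 at N=400 the optimum averages DSI 20.1, with apparent sensitivity 0.889 against 0.955 and NLR 0.164 against 0.084. It shows the lower NLR in 8.0% of trials (15.2% at N=250). In the recentred version its averages are still worse (0.876 against 0.900; 0.218 against 0.200), though it shows the lower NLR in 37% of trials at N=400 and 43% at N=250. There the bias mainly narrows 18.3's advantage.
- *A reader might infer that every selection rule produces the bias.* Sensitivity never rises with the cutoff, so a literal highest-sensitivity rule with ties to the lowest value always returns 13. That has no optimism, at specificity of only about 0.19 to 0.22.
- *The analysis is exploratory.* The validation decision does not use it, and insert use is a possibility, not a commitment.
- *The Youden bias is modest beside sampling error:* in Model 1 at N=400, about half the optimum's trial-to-trial SD of 5.2 to 6.1 points.

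None of this removes the bias in the selected cutoff's own estimate or its contrast with 18.3. The planned 95% CIs do not correct for it either.

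**Conclusion.** The concern holds in a limited form. Under the Youden rule, or the NPV/FNR rule with ties to the highest cutoff, the plan gives a favourably biased estimate for the cutoff it singles out, and a biased contrast with 18.3. At N=400 Youden overstates sensitivity by about 2.5 points and understates NLR by about 0.04. The NPV/FNR rule overstates sensitivity by about 1 point and shows an NLR at about half the truth or less. Both are worse at N=250.

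The sizes rest on normal DSI distributions anchored to only 22 HALT-C cases and to the design values. The NPV/FNR figures also depend on tie handling, which the plan leaves open; ties to the lower cutoff shrink the bias. The documents do not support reading this as a threat to the primary conclusion or to the fixed grid rows, or as a plan to promote a replacement cutoff.

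**What to change.** In Sections 1.1, 4.3.2 and 9.6.2:

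1. State one selection rule, including how ties are broken, and one search range.
2. For the selected cutoff, report bootstrap optimism-corrected sensitivity, specificity and NLR, repeating the whole selection in each of at least 1,000 resamples.
3. Base the comparison with 18.3 on the corrected values.
4. Label any data-selected cutoff as exploratory and not validated, in the report and in any labelling table.

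The cost is a few lines of SAP text and one program. Sample size, conduct and the primary analysis do not change. The downside is that the exploratory figures become slightly less favourable. A label alone would be cheaper and would meet much of the concern, but it would leave the numerical contrast with 18.3 uncorrected.

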¹ NOTE: There is some disagreement in the literature regarding the calculation of the False Negative Rate (FNR) for a test. FNR has been defined by the U.S. Food and Drug Administration in a disease-centric manner as 1 - Sensitivity ((Σ False negative) / (Σ Condition positive)), while being defined in much of the clinical literature in a test-centric manner as 1- NPV ((Σ False negative) / (Σ Predicted condition negative)). To compare to published results from the literature, in this protocol, the test-centric definition for FNR (1-NPV) has been used, and the term "miss rate" has been used to express 1-Sensitivity.

population is 20%. Each subject will have been selected to undergo a future EGD for variceal screening or surveillance according to standard criteria used in current clinical practice.

Enrolled subjects will undergo standard clinical assessment, laboratory tests, and the HepQuant SHUNT Test. The previously scheduled EGD will be performed no more than 6 weeks following the HepQuant SHUNT Test.

The relationship of DSI to large varices will be analyzed by AUROC and the diagnostic performance of the DSI cutoff \leq 18.3 will be defined by sensitivity, specificity, PPV, NPV, NLR, PLR, FNR and miss rate². The validated DSI cutoff will aid the clinician in the decision to proceed with or avoid the EGD.

Objectives:

The **primary objective** of this study is to validate DSI ≤18.3 for identifying subjects with CLD selected for future EGD for variceal screening or surveillance who are not likely to have large esophageal varices if the EGD were to be performed ("Rule Out").

The Secondary objective is to define the relationship of DSI to probability for large varices over the full range of DSI.

Exploratory objective 1 is to examine the diagnostic performance of DSI for large varices over the full range of DSI. We will generate and evaluate the AUROC (c-statistic) for DSI in likelihood of large esophageal varices. The AUROC for DSI in likelihood of large varices will be compared to the c-statistic 0.76 reported by Abrades, et al, for LSM plus platelet count (8).

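### The exploratory rule for an optimal rule-out DSI favours low cutoffs, often gives no single answer, and conflicts with the Youden definition and with the search range stated elsewhere

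*Combined protocol and SAP*

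**What the plan says.** The rule appears three times in the combined protocol and SAP: Section 1.1 (Exploratory objective 1), Section 4.3.2 and Section 9.6.2. Each defines the optimal rule-out cutoff by "highest sensitivity and NPV with lowest FNR" and then compares that cutoff with 18.3. None of the three adds a minimum specificity, a weighting or a tie-break.

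The search range is not the same throughout. Section 4.3.2 reads "We will examine, in 0.5 increments of DSI, DSI's diagnostic performance" and continues, after a list of measures, "from 13 to 23 to define the Optimal DSI for" rule-out. Section 9.6.2 works "over the full range of DSI to define the Optimal DSI for" rule-out.

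The footnote in Section 1.1 says that "the test-centric definition for FNR (1-NPV) has been used".

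Section 4.3.2 also carries a second criterion. Its ROC step says "The optimum performance characteristics will be defined by Youden Index", and the paragraph that contains the 13-to-23 search ends with the detached clause "as defined from AUROC analysis and Youden Index".

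The status is clear: "An exploratory objective is to examine the diagnostic performance of DSI cutoff 18.3" against neighbouring cutoffs. Sections 4.3.2 and 9.6.2 add that the resulting table could go into a package insert.

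**The concern.** A rule for choosing a cutoff has to trade something off. This one lists three quantities, but FNR = 1 − NPV makes the last two identical, so only sensitivity and NPV remain. Sensitivity cannot fall as the cutoff is lowered. Nothing in the rule directly credits specificity, which is what determines how many unnecessary EGDs are avoided. The intended use in Section 1.1 is to help the clinician proceed with or avoid EGD, so the rule leaves out half of the purpose.

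At stake is which cutoff is reported as optimal beside 18.3. With ties, two definitions of optimum and two ranges, that choice would be made after the data are seen.

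**Working it through.** **1. Reproduce the plan's HALT-C figures at 18.3.** Table 2 gives TP 21, FN 1, FP 89, TN 106.
- Sensitivity 21/22 = 0.955
- Specificity 106/195 = 0.544
- NPV 106/107 = 0.991, so FNR = 0.009
- Share at or below the cutoff 107/217 = 0.49

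These match the stated 95%, 54%, 99%, 1% and 49% of EGDs avoided.

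**2. Direction of each term.** Sensitivity at cutoff c is P(DSI > c | large varices). It cannot rise as c rises, so the lowest cutoff examined always attains the maximum, alone or tied. HALT-C shows the pull. In Table 3 a predicted probability of 0.10 corresponds to DSI = (6.4682 − 2.1972)/0.1947 = 21.9. Below that, Table 5 has 154 patients, 6 of them with large varices. Moving from 18.3 to 21.9 takes sensitivity from 0.955 to 16/22 = 0.727, and NPV from 0.991 to 148/154 = 0.961.

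**3. Observed NPV is not monotone.** Take 80 cases and 320 non-cases, with one case below 13 and none between 13 and 18.5. Sensitivity is 79/80 = 0.9875 throughout. If specificity rises from 80/320 = 0.25 to 172/320 = 0.54 (assumed), NPV rises from 80/81 = 0.988 to 172/173 = 0.994. Of the cutoffs from 13 to 18.5, the rule then prefers 18.5.

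**4. Apply the rule to HALT-C on the 0.5 grid.** There is one miss at 18.3, so every grid cutoff from 13 to 18 has at most one miss. The result depends on where that one patient's DSI lies, which the documents do not give:
- At or below 13: sensitivity is 21/22 at every cutoff from 13 to 18, NPV = TN/(TN + 1) cannot fall as the cutoff rises, and the top of that run is favoured.
- Above 13 and up to 13.5: cutoff 13 wins alone.
- Above 13.5: 13, 13.5 and possibly more cutoffs tie at 100% sensitivity and 100% NPV, and the rule picks none of them.

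**5. Apply the rule over the full range (Section 9.6.2).** Provided the lowest-DSI subject has no large varices, every cutoff from that subject's DSI to just below the lowest-DSI case scores sensitivity 100%, NPV 100% and FNR 0. Any cutoff that misses one case is rejected, and those that miss none are not separated. On the same proviso, 18.3 would fail this rule in its own training data.

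**6. Simulation on the 21-point grid.** Five models with normal DSI in each group were matched to AUROC 0.82 and specificity 0.54 at 18.3. Prevalence was 20%, N=400, with 5,000 trials each. The normal shape and the SDs are assumptions.

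| Sensitivity at 18.3 / SD without large varices | Maximum sensitivity tied | 13 sole best on both | 13 among joint best | NPV higher above 13 | No cutoff best on both |
|---|---|---|---|---|---|
| 0.88 / 6.65 | 69% | 26% | 36% | 64% | 10% |
| 0.90 / 6.65 | 77% | 21% | 48% | 52% | 4% |
| 0.90 / 5 | 84% | 15% | 67% | 33% | 3% |
| 0.95 / 6.65 | 96% | 4% | 91% | 9% | 0.1% |
| 0.95 / 5 | 98% | 2% | 98% | 2% | 0.2% |

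Cutoff 13 reached maximum sensitivity in every trial. The Youden Index chose 13 in none.

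**7. Cost of a low choice.** Across these models specificity at 13 is 0.17 to 0.25, against 0.56 at 18.5. In the first model the share testing negative is 0.8 × 0.246 + 0.2 × 0.024 = 0.20 at 13, and 0.8 × 0.556 + 0.2 × 0.124 = 0.47 at 18.5.

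**The case against.** A reader might infer that the rule must return the lowest cutoff whatever the data show. The documents do not support that. Only sensitivity is monotone. NPV in a sample can peak above 13, and steps 3, 4 and 6 show the data moving the choice upward or leaving it open.

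A reader might also infer that the table proposed for the package insert is compromised. It is not. It lists performance cutoff by cutoff, including specificity, and does not depend on which row is called optimal.

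It can further be said that the section does bring in specificity, through the Youden Index, and that weighting sensitivity is deliberate, since Section 4.3.1 sets the goal of excluding every case with large varices. The second argument is fair as a preference, but it does not justify a rule with no tie-break and a duplicated term. The first describes a second, different definition. The sentences that state the rule do not mention Youden, and Sections 1.1 and 9.6.2 do not tie it to this choice. Because Youden never chose 13 in the simulations while 13 was often among the joint best under the written rule, the two definitions can disagree, and the text does not say which governs.

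**Conclusion.** The concern holds in this form: the exploratory optimum is poorly defined and leans low. The rule counts NPV twice, gives specificity no direct credit, and has a sensitivity term that the lowest cutoff always meets. On the 13-to-23 grid it often gives ties, and sometimes no cutoff is best on both terms (0.1% to 10% of trials). Over the full range it normally accepts only cutoffs that miss no case, a limit set by the single lowest-DSI patient with large varices. It also conflicts with the Youden definition in Section 4.3.2, and the two stated ranges differ.

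The arguments on monotonicity, ties and the duplicated term need no model; the full-range result needs only the proviso in step 5. The percentages rest on assumed normal DSI distributions and 20% prevalence.

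The importance is low. The primary test uses the fixed cutoff 18.3 and is unaffected, as is the cutoff-by-cutoff table. What changes is which cutoff is reported as optimal.

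**What to change.** Use one rule in Sections 1.1, 4.3.2 and 9.6.2: the highest specificity among cutoffs whose observed sensitivity meets a prespecified floor. The floor could be the 0.85 already required for the primary goal, or a stricter value that the sponsor states in advance. With 80 cases, 0.85 allows 80 − 68 = 12 misses, so the floor carries the clinical judgement and should be fixed before linked DSI and EGD results are seen. If two cutoffs tie on specificity, take the lower one.

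State one search range, and add 18.3 as a row, because it does not lie on a 0.5 grid starting at 13. Say explicitly that the Youden Index is descriptive only, and remove or attach the loose clause in Section 4.3.2. Because the cutoff would be chosen and assessed on the same data, report bootstrap optimism-corrected performance for it.

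The cost is a few lines of wording, one bootstrap run, and a decision on the floor in advance.
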